6.2 PIMASERTIB

The drug substance pimasertib (recommended international non-proprietary name [INN]; also known as MSC1936369B or AS703026) is a biaryl amine derivative. Its chemical name according to International Union of Pure and Applied Chemistry (IUPAC) is N-[(2S)-2,3-dihydroxypropyl]-3-[(2-fluoro 4-iodophenyl) amino] isonicotinamide hydrochloride.

Pimasertib is formulated as 15mg and 30mg (as free base) hard gelatin size 0 capsules for oral administration. Each of the strengths of pimasertib is presented in a different color capsule (see below).

1. 15mg: Green
2. 30mg: Gray

Capsules consist of pimasertib combined with the following inactive ingredients: lactose, microcrystalline cellulose, croscarmellose sodium, poloxamer 188, and magnesium stearate.

Pimasertib drug product is manufactured according to Good Manufacturing Practices (GMP).

Pimasertib will be provided for clinical use by EMD Serono as capsules packaged in amber glass bottles with high-density polyethylene (HDPE) caps, supplied in individual cardboard boxes.

Each box and drug unit will be numbered to allow complete drug accountability.

All drugs will be supplied with Certificates of Analysis. Packaging and labeling will be in accordance with applicable local regulatory requirements and applicable GMP Guidelines.

It is stored at room temperature ($\leq 25^{\circ}\text{C}/77^{\circ}\text{F}$).

Please note that drug disposal will be on site according to MDACC Institutional policy.

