	
 • In case of alternative explanations, hold study treatment until the event recovers to Grade ≤ 1
Grade 4	
 • Treatment must be permanently discontinued if no alternative explanation is identified.
Tumor Bleeding	
Grade ≥ 2	
 • Study treatment must be held till the event recovers to Grade ≤ 1 • Permanently discontinue treatment if the Investigator considers the participant to be at risk for additional severe bleeding.

Ocular toxicity

If a subject experiences Retinal Vein Occlusion the pimasertib treatment must be immediately stopped. Appropriate follow-up and treatment measures must be taken by the treating ophthalmologists.

If a subject shows a symptomatic serous retinal detachment: Withhold treatment for ≤ 3 weeks, if improved to grade 0/1, resume at same dose level. If not improved, resume at the lower dose level or permanently discontinue pimasertib treatment. Management should be discussed with Principal Investigator and ophthalmologist.

Elevation of Serum Creatine Phosphokinase

Subjects should be advised to immediately report any muscle pain, tenderness or weakness, or any macroscopic myoglobinuria (tea-colored urine). Subject-reported muscle symptoms or urine discoloration should be investigated with CPK measurements and urinalysis for myoglobinuria.

CPK measurement should be at screening and every 4 weeks; at any time for symptomatic patients. Assess with differentiation if irAE or due to Pimasertib; including DD presence/absence of further symptomatic findings: full history (including commeds), exercises, training, muscular injury, muscular injections, CPK isoenzymes, and etc.

CPK increase G4: Withhold pimasertib treatment for ≤ 3 week

Any CPK elevation and myalgia: If improved to grade ≤ 3 , resume at lower dose level, if not improved within 3 weeks, permanently discontinue pimasertib treatment.

Dehydration

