6.2.5 RESUMPTION OF TREATMENT AFTER DOSE DELAY

Patients may resume therapy at the same doses after dose interruption as long as they continue to meet the treatment safety parameters.

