8.11 SUPPORTIVE CARE GUIDELINES

Subjects should receive appropriate supportive care measures as deemed necessary by the treating principal investigator. Suggested supportive care measures for the management of adverse events with potential immunologic etiology are outlined below. Where appropriate, these guidelines include the use of oral or intravenous treatment with corticosteroids as well as additional anti-inflammatory agents if symptoms do not improve with administration of corticosteroids. Note that several courses of steroid tapering may be necessary as symptoms may worsen when the steroid dose is decreased. For each disorder, attempts should be made to rule out other causes such as metastatic disease or bacterial or viral infection, which might require additional supportive care. The treatment guidelines are intended to be applied when the principal investigator determines the events to be related to pimasertib and bintrafusp alfa (M7824).

Note: if after the evaluation the event is determined not to be related, the principal investigator does not need to follow the treatment guidance (as outlined below). Refer to Section for dose modification.

It may be necessary to perform conditional procedures such as bronchoscopy, endoscopy, or skin photography as part of evaluation of the event.

- **Pneumonitis:**
 - For **Grade 2 events**, treat with systemic corticosteroids. When symptoms improve to Grade 1 or less, steroid taper should be started and continued over no less than 4 weeks.
 - For **Grade 3-4 events**, immediately treat with intravenous steroids. Administer additional anti-inflammatory measures, as needed.
 - Add prophylactic antibiotics for opportunistic infections in the case of prolonged steroid administration.
- **Diarrhea/Colitis:**

Subjects should be carefully monitored for signs and symptoms of enterocolitis (such as diarrhea, abdominal pain, blood or mucus in stool, with or without fever) and of bowel perforation (such as peritoneal signs and ileus).

- All subjects who experience diarrhea/colitis should be advised to drink liberal quantities of clear fluids. If sufficient oral fluid intake is not feasible, fluid and electrolytes should be substituted via IV infusion. For Grade 2 or higher diarrhea, consider GI consultation and endoscopy to confirm or rule out colitis.
 - For **Grade 2 diarrhea/colitis**, administer oral corticosteroids.

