 - For **Grade 3-4** events, treat with intravenous corticosteroids for 24 to 48 hours.
 - When symptoms improve to Grade 1 or less, a steroid taper should be started and continued over no less than 4 weeks.
- **Renal Failure or Nephritis:**
 - For **Grade 2** events, treat with corticosteroids.
 - For **Grade 3-4** events, treat with systemic corticosteroids.
 - When symptoms improve to Grade 1 or less, steroid taper should be started and continued over no less than 4 weeks.
- **Ocular reactions:**
 - Visual disturbances: for Grade 2 events, pimasertib should be discontinued until full resolution of the event and recovery of vision, assuming resolution of the event within 2 weeks to Grade 1 or less.
 - In case of visual symptoms but without vision loss, the treatment will not be discontinued.
- **Skin reactions:**
 - Early introduction of oral tetracyclines and medium to high potency topical treatment (such as 1% hydrocortisone cream with moisteriser) should be initiated in case of Grade 1 or 2 skin reaction. The dose of the investigational treatment should not be decreased.
 - If a subject experiences a severe skin reaction (Grade ≥ 3), pimasertib therapy must be interrupted and may be resumed at the original dose when the reaction has resolved to Grade 1 or 2. In case of second or third occurrence of severe skin reaction pimasertib therapy must again be interrupted. Treatment may only resume at a lower dose level (45 mg BID after the second occurrence and 30 mg BID after the third occurrence) if the reaction has resolved to Grade 1 or 2. In case of further recurrence another dose reduction may be proposed.

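### The fixed pimasertib doses in the 8.11 skin-reaction rule are a reduction at each step only for a patient assigned 60 mg BID

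*Combined protocol and SAP*

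**What the plan says.** The skin-reactions bullet in Section 8.11 handles Grade 3 or worse reactions by occurrence. After the first, pimasertib is interrupted and "may be resumed at the original dose when the reaction has resolved to Grade 1 or 2". After the second and third it is interrupted again, and "Treatment may only resume at a lower dose level (45 mg BID after the second occurrence and 30 mg BID after the third occurrence"), subject to the same resolution criterion. Beyond that: "In case of further recurrence another dose reduction may be proposed". The bullet does not limit these doses to patients on 60 mg.

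The assigned dose varies. Section 6.2.1 allows 30, 45 or 60 mg BID and sets 45 mg as the Phase I starting dose. Sections 3.0 and 9.1 define DL1 as 45 mg, DL2 as 60 mg and the fallback DL-1 as 30 mg, and define no level below 30 mg.

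The other pimasertib reduction rules are relative. In Section 6.2.3 the rule for symptomatic serous retinal detachment reads "If not improved, resume at the lower dose level or permanently discontinue pimasertib treatment". The CPK rule tells an improved patient to "resume at lower dose level, if not improved within 3 weeks, permanently discontinue pimasertib treatment". Section 6.2.5 says generally: "Patients may resume therapy at the same doses after dose interruption as long as they continue to meet the treatment safety parameters".

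**The concern.** A rule that permits a restart only at a reduced level should give a reduced level to every patient it covers. This one prints two absolute doses that suit a single starting dose, and that is not the dose at which the trial starts. A site that follows the printed number would restart a 45 mg patient without any reduction after a second severe skin reaction. A patient assigned 30 mg has no usable step at all. What is at stake is the safety of individual patients with recurrent severe skin toxicity, and uniform handling of them.

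**Working it through.** **Inputs.** Assigned doses of 60, 45 and 30 mg BID (6.2.1, 9.1). Printed restart doses of 45 mg after the second occurrence and 30 mg after the third (8.11). Because the first occurrence restarts at the original dose, a patient not reduced for another reason is on the assigned dose when the second occurrence happens.

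**Check.** Change = printed dose / assigned dose − 1.

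| Assigned (mg BID) | Second occurrence | Third occurrence | Below the assigned dose? |
|---|---|---|---|
| 60 | 45/60 = 0.75, −25% | 30/60 = 0.50, −50% | Both steps |
| 45 | 45/45 = 1.00, 0% | 30/45 = 0.667, −33% | Third only |
| 30 | 45/30 = 1.50, +50% | 30/30 = 1.00, 0% | Neither |

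**Following the words instead of the figures** (one defined level down each time):

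- Assigned 60: 45, then 30. This matches the printed figures.
- Assigned 45: 30, then no defined level. The printed third-occurrence figure would then equal the current dose.
- Assigned 30: no defined level at either step.

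**Whether other text repairs it.**

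- 6.2.5 allows the same dose after an interruption, so it does not correct the 45 mg figure.
- 6.2.3 has no pimasertib skin rule; its rash paragraph concerns bintrafusp alfa lesions.
- The pointer in 8.11 to dose modification gives no section number.
- The further-recurrence sentence names no dose.

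**Patients at a dose where a printed step does not fit**, from the 3+3 rule (3 to 6 at a level) and Section 9.2 (6 from Phase I plus up to 24):

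- RP2D 60 mg: the 3 to 6 patients treated at 45 mg.
- RP2D 45 mg: up to 6 + 24 = 30 patients, for whom only the second-occurrence figure fails.
- RP2D 30 mg: up to 30 patients at 30 mg, plus those treated at 45 mg before de-escalation.

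These are counts by assigned dose, not forecasts of how many patients will have repeated severe skin reactions.

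**The case against.** The strongest reply is that the sentence already governs. It permits a restart only at a reduced level, so restarting at the same or a higher dose would breach it, and the parenthesis is an illustration written with a 60 mg start in mind. Much of this stands. A 45 mg patient's next level can be inferred as 30 mg. A reader might infer from the +50% in the table that a 30 mg patient would be escalated. The documents do not support that, because the governing words forbid it. What remains is that the investigator must override a printed number in a safety rule, and that at 30 mg there is nothing to infer.

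A second reply is that the section is advisory: "Suggested supportive care measures for the management of adverse events with potential immunologic etiology are outlined below". That, and the single study centre, limit the practical risk. But this bullet makes interruption mandatory and restricts the restart, so it reads as an instruction.

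Third, the missing level below 30 mg is not peculiar to 8.11. That is correct. Under the CPK rule a patient who improves resumes one level down, and discontinuation applies only if there is no improvement, so a 30 mg patient meets the same gap. The retinal rule does offer discontinuation as an alternative.

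A reader might also infer that every treated patient is affected if the RP2D is 30 mg. That would require DL2 never to have been opened, which the documents do not settle. Nor do the 60 mg entries in Table 1 and Table 3 footnote c imply misdosing: both places also print the 30 to 60 mg range.

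**Conclusion.** The inconsistency holds, as a minor point. The printed doses reduce at each step only from 60 mg BID. At 45 mg the second-occurrence figure is no reduction, and at 30 mg neither figure is. Because the first cohort is always at 45 mg, the text misfits some assigned doses whichever dose becomes the RP2D. Whether any patient reaches the rule depends on a second Grade 3 or worse skin reaction, for which the documents give no rate. The conclusion rests on the printed text and needs no assumed toxicity rate. It does not show that patients would be escalated, and it implies no effect on the design, DLT counts, stopping boundaries or analysis.

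**What to change.** In 8.11, replace the parenthesis with a relative step: one dose level below the dose at which the reaction occurred, that is 60 to 45 and 45 to 30 mg BID. Tying it to the dose at the time of the reaction also covers a patient already reduced under 6.2.3.

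State that a patient whose severe reaction recurs at 30 mg BID permanently discontinues pimasertib, or follows another explicit rule that the sponsor sets. A 15 mg BID level could be supplied ("Pimasertib is formulated as 15mg and 30mg (as free base) hard gelatin size 0 capsules for oral administration"), but it would be a new dose in this protocol and a clinical decision.

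Delete the sentence on further recurrence or align it; left as it stands, it would contradict the floor. Apply the same floor to the lower-level wording in 6.2.3 for retinal detachment and CPK.

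The cost is a few sentences in two sections, with no change to the design, sample size or analysis. The fix is also a change of treatment policy: some patients reach discontinuation one occurrence earlier than the printed text allows. For example, a patient assigned 45 mg would stop at the third occurrence, where the text now permits 30 mg. The sponsor should accept that explicitly.

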8.12 PATIENT DISCONTINUATION

THE PRIMARY REASON FOR STUDY TREATMENT DISCONTINUATION SHOULD BE DOCUMENTED IN THE SUBJECT'S CHART. PATIENTS WHO DISCONTINUE STUDY TREATMENT PREMATURELY WILL NOT BE REPLACED. PATIENTS WHO DISCONTINUE FROM TREATMENT WILL BE ASKED TO RETURN TO THE CLINIC NO MORE THAN 30 DAYS AFTER THE LAST TREATMENT FOR A TREATMENT DISCONTINUATION VISIT. THE

VISIT AT WHICH A RESPONSE ASSESSMENT SHOWS PROGRESSIVE DISEASE MAY BE USED AS THE TREATMENT DISCONTINUATION VISIT **8.13**

WITHDRAWAL

Subjects who discontinue/withdraw from treatment prior to completion of the treatment regimen should be encouraged to continue to be followed for all remaining study visits. However, patients have the right to voluntarily withdraw from the study at any time for any reason. In addition, the principal investigator has the right to withdraw a patient from the study at any time. Reasons for withdrawal from the study may include, but are not limited to the following:

- Patient withdrawal of consent at any time
- Any medical condition, determined by the principal investigator that may jeopardize the patient's safety if he or she continues in the study
- Patient becomes pregnant
- Principal Investigator determines it is in the best interest of the patient
- Patient non-compliance

When a subject discontinues/withdraws from participation in the trial, all applicable activities scheduled for the final trial visit should be performed at the time of discontinuation. Any adverse events which are present at the time of discontinuation/withdrawal should be followed in accordance with the safety requirements.

8.14 END OF STUDY

The end of this study is defined as the date when the last patient, last visit (LPLV) occurs or the date at which the last data point required for statistical analysis or safety follow-up is received from the last patient, whichever occurs later. LPLV is expected to occur 24 months after the last patient is enrolled in the trial.

8.15 POST STUDY DRUG FOLLOW UP

In this study, clinical benefit rate is the primary endpoint of the study. Post study follow-up is of critical importance and is essential to preserving subject safety and the integrity of the study.

Subjects who discontinue study drug must continue to be followed for collection of outcome and/or survival follow-up data as required by phone every 12 weeks until death or the conclusion of the study.

8.16 LOST TO FOLLOW-UP

All reasonable efforts must be made to locate subjects to determine and report their ongoing status. This includes follow-up with persons authorized by the subject as noted above. Lost to follow-up is defined by the inability to reach the subject after a minimum of three documented phone calls, faxes, or emails as well as lack of response by subject to one registered mail letter.

All attempts should be documented in the subject's medical records. If it is determined that the subject has died, the site will use permissible local methods to obtain the date and cause of death.

The site staff and PI will consult publicly available sources, such as public health registries and databases, in order to obtain updated contact information. If after all attempts, the subject remains lost to follow-up, then the last known alive date as determined by the principal investigator should be reported and documented in the subject's medical records

9.0 STATISTICAL CONSIDERATIONS

9.1 PHASE I

The phase I dose finding part of the study is to determine the recommended phase II dose (RP2D) of Bintrafusp Alfa (M7824) + Pimasertib in patients with intracranial metastasis. The planned DL1 and DL2 doses are Bintrafusp Alfa (M7824) flat dose of 1200 mg every 2 weeks and Pimasertib 45 mg PO BID (DL1) and 60 mg PO BID (DL2), and fallback doses DL-1 are Bintrafusp Alfa (M7824) flat dose of 1200 mg every 2 weeks and Pimasertib at 30 mg PO BID. We will enroll up to 12 patients to the Phase I portion (up to 18 can be enrolled should the trial de-escalate to DL-1). The standard “3+3” design will be employed to determine the RP2D. If DL1 is considered too toxic, DL-1 will be explored, if unacceptable toxicity is observed at DL-1, we will consider alternative schedules in discussion with EMD Serono.

Dose limiting toxicity (DLT) is defined as below, including an intracranial and an extracranial DLT. These will be evaluated **at 4 weeks** after first administration of treatment.

Intracranial DLT (T1): Hypophysitis Grade ≥ 3 ; or neurologic toxicity Grade ≥ 3

Extracranial DLT (T2): Any Grade ≥ 3 adverse event outside CNS that is related to Bintrafusp Alfa (M7824) or Pimasertib, occurring during the DLT evaluation period

(Exceptions include: grade 3 flu-like symptoms or fever lasting less than a week, Grade 3 fatigue lasting less than a week, local reactions, headaches, nausea, and emesis lasting less than 72 hours, and grade 3 hemoglobin decrease ($<8.0\text{g/dL}$)).

Elevated alanine aminotransferase (ALT) or aspartate aminotransferase (AST) 3 times the upper limit of normal (ULN) range and a concomitant elevation of bilirubin 2 times the ULN attributable to study drug constitutes a DLT.

The first cohort of 3 patients will be treated at Dose Level 1. New cohorts of patients will not be treated until toxicity has been fully evaluated for all current patients.

The algorithm is as follows at any dose level:

1. If 0 out 3 patients experiences DLT, the next cohort of 3 patients will be treated at the next higher dose level.
2. If 1 out of 3 patients experiences DLT, additional 3 patients will be treated at the same dose level. If no more than 1 out of 6 patients experiences DLT, the next cohort of 3 patients will be treated at the next higher dose level.
3. At any time, if greater than or equal to 2 out 3 or greater than or equal to 2 out 6 patients experience DLT, another 3 patients will be treated at the next lower dose level if no more than 3 patients have been treated at the lower dose level.

Proprietary Information of MD Anderson

The recommended phase II dose (RP2D) is defined as the highest dose level with no more than 1 patient with DLT out of 6 patients that are treated.

9.2 PHASE II

The purpose of phase II part is to estimate the time to intra-cranial progression and overall survival time. In this part, we will enroll up to additional 24 patients into RP2D over the course of 12-18 months. The 6 patients treated at RP2D from phase I part of the study will be included in the Phase II part, thus resulting in a total of 30 patients at RP2D by the end of the study, with the goal of having 10 patients with each of melanoma, NSCLC, and breast cancer. This phase II part is designed to collect data for future larger studies. Specifically, we would like to estimate time to intracranial progression considering death as a competing risk and overall survival time using Kaplan-Meier method, both with 95% confidence interval.

Two dose limiting toxicities (DLT) will be monitored separately: intracranial and extracranial DLTs. If there is a high chance that probability of intracranial DLT is found to be $> 15\%$, i.e., $\text{Pr}(\text{intra-cranial DLT Rate} > 15\% | \text{Data}) > 70\%$, or the extra-cranial DLT rate of higher than 30% , i.e., $\text{Pr}(\text{extra-cranial DLT Rate} > 30\% | \text{Data}) > 70\%$, then the regimen will be considered too toxic at current dose. Results should be discussed with EMD Serono to decide if further enrollment should be started at a lower dose level. Protocol will be amended if necessary. The window for DLT evaluation will be at 4 weeks after the start of the treatment.

Given these rules and the prior for intra-cranial DLT toxicity rate as $\text{beta}(0.15, 0.85)$ and extra-cranial DLT toxicity rate as $\text{beta}(0.3, 0.7)$, we claim a dose level too toxic if any of the following happens.

Number of patients with intra-cranial DLTs/total of number of patients treated $\geq 3/10, 4/15, 5/20, 5/25, 6/30$; or

Number of patients with extra-cranial DLTs/total of number of patients treated $\geq 4/10, 6/15, 8/20, 9/25, 11/30$.

The operating characteristics based on the toxicity stopping rules for 30 patients are in Table 4. The Bayesian toxicity monitoring rule are calculated by the online Shiny application Bayesian Toxicity Monitoring using posterior probability developed by Department of Biostatistics. The operating characteristics were evaluated using codes written by statistical collaborator [name].

Table 4: Operating Characteristics (5,000 simulations)

True Intracranial DLT Rate	True Extracranial DLT Rate	P (Stop Early)	Average of Expected Sample Size
0.05	0.1	0.03	29
0.05	0.2	0.17	27
0.05	0.3	0.50	22
0.05	0.4	0.82	16
0.05	0.5	0.97	12

Proprietary Information of MD Anderson

0.15	0.1	0.38	25
0.15	0.2	0.47	23
0.15	0.3	0.68	19
0.15	0.4	0.88	14
0.15	0.5	0.98	11
0.30	0.1	0.93	14
0.30	0.2	0.94	13
0.30	0.3	0.96	12
0.30	0.4	0.99	11
0.30	0.5	>0.99	10

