9.3.8 OTHER ENDPOINTS

Descriptive analysis will be provided to summarize the serum, tissue and imaging markers. The relationship between the markers and response and/or toxicities may be evaluated using Kruskal-Wallis test for continuous markers and Fisher's exact test for discrete markers, when appropriate. The correlation between the serum/tissue markers and imaging parameters or between any two markers may also be assessed using Spearman correlation. Given the size of the study, these analysis are exploratory in nature.

Other statistical analysis methods may be applied when fit.

The Principal Investigator is responsible for completing toxicity/efficacy summary reports and submitting them to the IND office Medical Affairs and Safety Group for review. These should be submitted as follows:

- Phase I:

After the first 3 evaluable patients, complete 4 weeks of study treatment, and every 3 evaluable patients thereafter, IND Office approval must be obtained prior to advancing/changing dose levels.

- Phase II:

After the first 10 evaluable patients(including the six treated at RP2D from phase I) complete 4 weeks of study treatment, and every 5 patients thereafter. Also, a toxicity report will be submitted per cohort.

A copy of the summary report should be placed in the Principal Investigator's Regulatory Binder under "sponsor correspondence".

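### Table 4 treats all 30 patients as unselected, but six come from phase I with at most one DLT patient among them, so once a dose is the RP2D the phase II toxicity rule stops less often and later than stated

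*Combined protocol and SAP*

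**What the plan says.** Section 9.1 defines the RP2D as the "highest dose level with no more than 1 patient with DLT out of 6 patients that are treated". DLT there covers both types: "Dose limiting toxicity (DLT) is defined as below, including an intracranial and an extracranial DLT", assessed at 4 weeks.

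Section 9.2 adds 24 patients and states that "The 6 patients treated at RP2D from phase I part of the study will be included in the Phase II part", for a total of 30. It monitors intracranial and extracranial DLTs separately with the same window: "The window for DLT evaluation will be at 4 weeks after the start of the treatment". The boundaries are at least 3/10, 4/15, 5/20, 5/25 and 6/30 intracranial, or at least 4/10, 6/15, 8/20, 9/25 and 11/30 extracranial.

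Section 9.3.8 times the first phase II report "After the first 10 evaluable patients(including the six treated at RP2D from phase I) complete 4 weeks of study treatment", then every 5 patients.

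Section 9.2 introduces the performance of the rule with "The operating characteristics based on the toxicity stopping rules for 30 patients are in Table 4". Table 4 gives the probability of stopping early and the average sample size for 15 pairs of true rates, from 5,000 simulations. The text does not describe the simulation model and does not mention the RP2D condition.

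**The concern.** When the phase II rule is first applied, six of the ten patients are already known to include at most one with any DLT. Those six can therefore add at most one intracranial and at most one extracranial event to counts that must reach 3 or 4. A simulation that draws all ten afresh lets the first six contribute more events than the RP2D rule permits, which inflates the chance of stopping, above all at the first look.

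Table 4 is the only quantitative account of phase II toxicity monitoring in the plan. Whoever judges whether that monitoring is adequate would read from it that a dose with true rates 0.15/0.40 is stopped in 88% of trials after about 14 patients. If that does not hold for a dose that has passed phase I, the sponsor and the IND Office would expect more of the phase II rule than it delivers.

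**Working it through.** **Inputs.** Priors beta(0.15, 0.85) and beta(0.3, 0.7), limits 15% and 30%, the 70% posterior cut-off, and the boundaries (all Section 9.2). RP2D rule and DLT definition (Section 9.1). Looks at 10 and every 5 thereafter, with the six phase I patients in the first ten (Section 9.3.8). Rates below are written as intracranial/extracranial.

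**Step 1: boundaries.** With k events in n patients the posterior is beta(a + k, b + n − k). The smallest k for which the posterior probability of exceeding the limit is above 0.70, at n = 10, 15, 20, 25 and 30, is 3, 4, 5, 5, 6 (intracranial) and 4, 6, 8, 9, 11 (extracranial). All ten match the plan.

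**Step 2: Table 4 as printed.** I used an exact recursion on the joint count of the two DLT types. It takes 30 independent unselected patients, the two types independent within a patient, and looks at 10, 15, 20 and 25. All 15 stopping probabilities come within 0.01 of Table 4 and all average sample sizes within 1 patient. Counting a crossing at 30 as an early stop does not reproduce the table (0.703 against the stated 0.68 at 0.15/0.30).

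**Step 3: the first look by hand, at 0.15/0.30.**

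- Unselected: P(at most 2 of 10 intracranial) = 0.820 and P(at most 3 of 10 extracranial) = 0.650. The chance of stopping is 1 − 0.820 × 0.650 = 0.467.
- Given the RP2D rule: a patient has no DLT with probability q = 0.85 × 0.70 = 0.595. P(at most 1 of 6 with any DLT) = q⁶ + 6(1 − q)q⁵ = 0.044 + 0.181 = 0.226 (before rounding the parts).
- Given a pass, the six contain no DLT patient (weight 0.197), one intracranial only (0.208), one extracranial only (0.506), or one patient with both (0.089).
- The chance that the next four patients leave both counts below the boundary is, in that order, 0.980, 0.883, 0.905 and 0.816. The weighted sum is 0.907.
- The chance of stopping at the first look is therefore 1 − 0.907 = 0.093, against 0.467.

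**Step 4: all looks.** This is the recursion of Step 2, restricted after patient 6 to at most one patient with any DLT. The two-stage figure is the probability that the dose fails the 1-in-6 rule or is later stopped: 1 − P(pass) × (1 − conditional stop). For 0.15/0.40 it is 1 − 0.119 × (1 − 0.612) = 0.954.

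| True rates | Table 4: stop, N | Given RP2D: stop, N | P(pass 1/6) | Two-stage |
|---|---|---|---|---|
| 0.05/0.10 | 0.03, 29 | 0.01, 29.9 | 0.788 | 0.219 |
| 0.05/0.20 | 0.17, 27 | 0.04, 29.4 | 0.558 | 0.465 |
| 0.05/0.30 | 0.50, 22 | 0.20, 27.5 | 0.348 | 0.723 |
| 0.05/0.40 | 0.82, 16 | 0.52, 23.5 | 0.190 | 0.910 |
| 0.05/0.50 | 0.97, 12 | 0.82, 18.8 | 0.088 | 0.984 |
| 0.15/0.10 | 0.38, 25 | 0.24, 27.4 | 0.570 | 0.567 |
| 0.15/0.20 | 0.47, 23 | 0.25, 27.2 | 0.378 | 0.716 |
| 0.15/0.30 | 0.68, 19 | 0.36, 25.7 | 0.226 | 0.857 |
| 0.15/0.40 | 0.88, 14 | 0.61, 22.5 | 0.119 | 0.954 |
| 0.15/0.50 | 0.98, 11 | 0.85, 18.4 | 0.054 | 0.992 |
| 0.30/0.10 | 0.93, 14 | 0.82, 19.2 | 0.283 | 0.950 |
| 0.30/0.20 | 0.94, 13 | 0.82, 19.4 | 0.176 | 0.968 |
| 0.30/0.30 | 0.96, 12 | 0.84, 18.9 | 0.100 | 0.984 |
| 0.30/0.40 | 0.99, 11 | 0.90, 17.6 | 0.051 | 0.995 |
| 0.30/0.50 | >0.99, 10 | 0.96, 15.6 | 0.022 | 0.999 |

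Six of each N are already treated when phase II starts. At 0.15/0.40 the average number of new patients is therefore 22.5 − 6 = 16.5, against 14 − 6 = 8 read from Table 4.

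A simulation of 400,000 trials in four of the scenarios agreed with the recursion to within 0.003 in stopping probability and 0.05 patients in N.

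**Step 5: sensitivity.** In the four rows with the largest gap (0.05/0.30, 0.05/0.40, 0.15/0.30, 0.15/0.40) the conditional stopping probabilities are 0.203, 0.523, 0.364 and 0.612 under independence. If the two DLT types never occur in the same patient they are 0.201, 0.519, 0.375 and 0.641. With maximal positive dependence they are 0.207, 0.529, 0.320 and 0.567. Counting a crossing at 30 under independence gives 0.226, 0.582, 0.411 and 0.675.

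**The case against.** The strongest reply is that nothing in Table 4 is miscalculated and that overall protection is not overstated. The table is correct for 30 unselected patients. A toxic dose must first pass phase I, which it seldom does (0.12 to 0.35 in the four rows with the largest gap), and the two-stage rejection probability exceeds Table 4 in every row: 0.91 against 0.82 at 0.05/0.40, and 0.86 against 0.68 at 0.15/0.30. At acceptable rates the conditional rule gives fewer false stops. Crossing a boundary leads to discussion rather than automatic closure, and the IND Office reports and monthly safety meetings are further safeguards. On this view one clarifying sentence is enough.

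Most of this is true and limits the point: it does not show that the trial as a whole protects patients less than claimed. It does not rescue the table. Table 4 is offered as the behaviour of the phase II rule, and that rule operates only on a dose that has passed the 1-in-6 screen. The two-stage probability is a different quantity, which the plan does not report.

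The reply also has force on the remedy. Conditional figures printed alone would make the design look weaker than it is, so the two-stage column should accompany them.

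**Conclusion.** The concern holds. Table 4 does not describe the phase II rule as applied to a declared RP2D. Given that selection, early stopping is less likely and later in all 15 rows. The gap is 27 to 32 points near or moderately above the limits, 13 to 15 points at extracranial 0.50 with intracranial 0.05 or 0.15, and about 4 to 12 points at intracranial 0.30, where the rule still stops in 82% to 96% of trials.

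The size rests on two assumptions. The two DLT types are taken as independent within a patient, which is the model that reproduces Table 4; the direction is the same under maximal positive dependence and the conditional figures are similar if the types are mutually exclusive. Passing phase I is taken to depend only on the six patients at that dose. The plan does not give the simulation code, so the use of unselected patients is inferred from the match in all 15 rows.

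This should be fixed, but it does not call the boundaries or the sample size into question.

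**What to change.** Keep the boundaries. Re-run the existing simulation with the first six patients drawn under the RP2D rule (at most 1 of 6 with any DLT). Preferably add the conditional stopping probability and average sample size beside the present columns, and label the present columns as unconditional. If the conditional figures replace the present columns instead, the two-stage column becomes essential. In either case add the two-stage probability (dose fails the 1-in-6 rule or is later stopped) as a further column.

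Add to Section 9.2: *The conditional figures apply to a dose already declared the RP2D, that is, with at most 1 of the first 6 patients having a DLT.* State there too that the two DLT types are simulated as independent, if the code confirms it, and that a crossing at 30 does not count as an early stop.

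The cost is one re-run, two or three columns and a few lines of text. The stated phase II stopping figures near the limits will look less favourable. No boundary, sample size or monitoring decision changes.
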